6.10. Primary Outcome and Methodology

The primary efficacy variable is the change from baseline in the weekly mean of the 24-hour average pain score measured using an 11-point NRS in the daily patient diary. The weekly mean of the 24-hour average pain score for each week will be the mean score for the following duration:

Week	Duration used for the calculation of weekly mean
Baseline	Day -6 to Day 0
1	Day 2 to 7
2	Day 8 to 14
3	Day 15 to 21
4	Day 22 to 28
5	Day 29 to 35
6	Day 36 to 42
7	Day 43 to 49
8	Day 50 to 56
9	Day 57 to 63
10	Day 64 to 70
11	Day 71 to 77
12	Day 78 to 84

A mixed-model repeated measures (MMRM) analysis will be the primary analytical technique to assess mean change in efficacy measures. The MMRM model will include the random effect of patient and fixed categorical effects of treatment, duration of DPNP (<2 years, ≥2years), week, and treatment-by-week interaction, as well as the continuous fixed covariates of baseline value. An unstructured covariance structure will be used to model the within-patient errors. A Kenward-Rogers correction (Kenward and Roger 1997) will be used to estimate denominator degrees of freedom.

The difference in LS mean between treatments (duloxetine minus pregabalin) at Week 12, along with its 2-sided 95% CI, will be calculated, based on the model. If the upper bound of the 95% CI does not exceed 0.51, it will be concluded that duloxetine is not inferior to pregabalin.

If the model with unstructured covariance structure fails to converge, the sandwich estimator be used to estimate the standard errors of the fixed effects parameters and the model will be fit using covariance structures of the following order until convergence is met:

- heterogeneous toeplitz type = toeph
- heterogeneous autoregressive (1st order) type = arh(1)
- heterogeneous compound symmetric type = cs(h)
- toeplitz type = toep
- autoregressive (1st order) type = ar(1)
- compound symmetric type = cs

If the sandwich estimator is used, the Kenward-Roger approximation for denominator degrees of freedom cannot be used; instead, the denominator degrees of freedom will be partitioned into between-subject and within-subject portions (denoted by DDFM= BETWITHIN in the MODEL statement).

An analysis of covariance (ANCOVA) model will be used to analyze the change from baseline to Week 12 in the weekly mean of the 24-hour average pain score measured using an 11-point NRS in the daily patient diary. The model will contain the main effects of treatment and duration of DPNP (<2 years, ≥2years) as well as the continuous fixed covariates of baseline value. The LS mean will be used for the statistical comparisons using ANCOVA.

For the imputation of the missing values, the following 2 methods: BOCF and LOCF will be used. Both analyses will be performed as a secondary analysis to examine the robustness of the primary analysis result.

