## 12.2. Statistical and Analytical Plans

#### 12.2.1. General Considerations

Statistical analysis of this study will be the responsibility of Eli Lilly.

Efficacy analyses will be conducted on the full analysis set (FAS). The FAS includes all data from all randomized patients receiving at least 1 dose of the study drug according to the treatment the patients were assigned. When mean change from baseline to endpoint is assessed, data will be included in the analysis only if there is a baseline and a corresponding postbaseline measure.

Analyses based on the per-protocol set (PPS) will be performed to examine the robustness of the primary efficacy analysis. The PPS will be defined as a subset of patients in FAS who did not have major protocol deviations.

Safety analyses will be conducted on the safety analysis set. This set includes all randomized patients who received at least 1 dose of study drug. Safety analyses will be based on the treatment the patients actually received.

All tests of hypotheses will be considered statistically significant if the 2-sided p-value is <0.05, unless otherwise stated. No adjustments for multiple comparisons will be made.

Any change to the data analysis methods described in the protocol will require an amendment ONLY if it changes a principal feature of the protocol. Any other change to the data analysis methods described in the protocol, and the justification for making the change, will be described in the clinical study report. Additional exploratory analyses of the data will be conducted as deemed appropriate.

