6.2. General Considerations

Statistical analysis of this study will be the responsibility of Eli Lilly. Analyses will be conducted using SAS 9.2 (or later).

Efficacy analyses will be conducted on the full analysis set (FAS), unless otherwise stated. The FAS includes all data from all randomized patients receiving at least 1 dose of the study drug according to the treatment the patients were assigned. When mean change from baseline to endpoint is assessed, data will be included in the analysis only if there is a baseline and a corresponding postbaseline measure.

Safety analyses will be conducted on the safety analysis set. This set includes all randomized patients who received at least 1 dose of study drug. Safety analyses will be based on the treatment the patients actually received.

Analyses based on the per-protocol set (PPS) will be performed to examine the robustness of the primary efficacy analysis. The PPS will be defined as a subset of patients in FAS who did not have major protocol deviations.

All tests of hypotheses will be considered statistically significant if the 2-sided p-value is <0.05 , unless otherwise stated. No adjustments for multiple comparisons will be made.

Any change to the data analysis methods described in the protocol will require an amendment ONLY if it changes a principal feature of the protocol. Any other change to the data analysis methods described in the protocol, and the justification for making the change, will be described in the SAP and clinical study report. Additional exploratory analyses of the data will be conducted as deemed appropriate.

Baseline value for a variable will be defined as the last non-missing value for this variable prior to or at randomization visit (Visit 2), unless otherwise specified.

The endpoint value for an efficacy variable is defined as the last non-missing post baseline value prior to or at Visit 6 (Week 12), unless otherwise stated.

The endpoint value for a safety variable is defined as the last non-missing post baseline value prior to or at Visit 7 (Week 13), unless otherwise stated.

In general, descriptive summary statistics will include:

- for categorical variables: number and percentage (with the percentage excluding the number missing in the denominator)
- for continuous variables: number, mean, median, standard deviation, minimum, and maximum.

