6.11. Efficacy Analyses

The secondary efficacy objectives will be addressed by conducting MMRM analyses (as described in [Section 6.10](#), but without the baseline score in the model for CGI-I and PGI-I, and week will be replaced by visit except for items from diary) to compare treatment differences for the following variables:

- From the BPI-SF, each of the 4 questions assessing the severity of worst pain, least pain, and average pain in the past 24 hours, and the pain right now
- From the BPI-SF, each of the 7 questions assessing the interference of pain with activities and the mean of the seven questions
- Weekly mean of night pain and worst pain scores measured using 11-point NRS in the daily patient diary
- BDI-II total score
- CGI-I and PGI-I

For the NPSI questionnaire, the total score and each of the 5 subscores: burning spontaneous pain, pressing spontaneous pain, paroxysmal pain, evoked pain, and paresthesias/dysesthesias will be addressed by ANCOVA analysis (as described in [Section 6.10](#)) to compare treatment differences. Missing data will be imputed using LOCF method.

Further secondary objectives will be addressed by comparing treatment groups with respect to the proportions of patients achieving each of the following at Visit 6 (Week 12) using Fisher's exact test. In this analysis, missing data will be imputed using LOCF method:

- A $\geq 30\%$ reduction on the weekly mean of the 24-hour average pain score measured using an 11-point NRS in the daily patient diary
- A $\geq 50\%$ reduction on the weekly mean of the 24-hour average pain score measured using an 11-point NRS in the daily patient diary

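### Does naming a random patient effect next to an unstructured covariance (SAP 6.10) put the primary analysis at risk?

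*SAP*

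**What the plan says.** SAP 6.10 defines the primary model: "The MMRM model will include the random effect of patient and fixed categorical effects of treatment". The other terms are duration of DPNP, week, treatment-by-week interaction and the baseline value. On correlation it adds: "An unstructured covariance structure will be used to model the within-patient errors". Weekly means are defined for Weeks 1 to 12, and degrees of freedom follow Kenward-Roger. Protocol 12.2.6 and the protocol synopsis carry the same pair of statements. Neither document says that the random effect is only descriptive, or that it is left out of the fit.

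The fallback begins: "If the model with unstructured covariance structure fails to converge". The plan then moves to sandwich standard errors and six simpler structures in order (TOEPH, ARH(1), CSH, TOEP, AR(1), CS). It also changes the degrees of freedom: "If the sandwich estimator is used, the Kenward-Roger approximation for denominator degrees of freedom cannot be used". The between-within method replaces Kenward-Roger.

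The secondary models in SAP 6.11 point back to this one: "The secondary efficacy objectives will be addressed by conducting MMRM analyses".

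**The concern.** A random patient intercept and an unstructured error matrix describe the same within-patient correlation. A programmer who coded both would fit a model whose covariance parameters are not all identified, so the information matrix for those parameters would be singular.

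That deserves a look because this model yields the one decisive number, the upper 95% bound compared with 0.51. Non-convergence also has planned consequences: another covariance structure, another standard error and another degrees-of-freedom method. If the redundant term stopped the fit, or produced a warning about the Hessian or the random-effects matrix that was taken for non-convergence, the primary bound would come from the fallback for no statistical reason.

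**Working it through.** **Inputs.** From SAP 6.10: 12 post-baseline weeks, one random patient effect, unstructured errors, Kenward-Roger, limit 0.51. From SAP 6.1: 286 patients, SD 1.82, assumed advantage 0.1, margin 0.51, one-sided 0.025, power 80%. The documents give no count of covariance parameters to reproduce.

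**The plan's own figure.** The sample size does not involve the covariance model. By the normal approximation, n per arm = 2 × (1.960 + 0.842)² × 1.82² / (0.51 + 0.1)² = 2 × 7.849 × 3.312 / 0.372 = 139.7, so 140. The noncentral t gives 80.1% power at 141 per arm. The plan's 141 is reproduced and is not at issue.

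**Parameter count.** Let R be the 12 × 12 error covariance, s the patient variance and J the all-ones matrix. The covariance of a patient's data is V = R + sJ.

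- R unstructured: 12 × 13 / 2 = 78 parameters.
- Adding s: 79 parameters.
- V has 78 distinct elements, so the rank is 78 and exactly one parameter is redundant.

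**Likelihood.** With s = 0, every positive definite V is available. With s > 0, V is still positive definite. Both models therefore allow the same set of V, and the likelihood depends on the covariance parameters only through V. The maximum, the fitted V and the fixed effects are the same. This also holds with missing weeks, because each patient contributes the matching sub-block of V.

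**Kenward-Roger.** V is linear in the parameters. Write V = Aθ, with A of full row rank. The information for θ is A′IA, and the gradient of the contrast variance is A′g, where I and g are the quantities for the plain 78-parameter model. With a generalized inverse, (A′g)′(A′IA)⁻(A′g) = g′I⁻¹g. The adjusted standard error and the df are therefore also the same. If the software instead sets s to zero, the plain model is fitted directly.

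**Numerical check.** One trial was simulated with 286 patients, 12 weeks and the SAP 6.10 fixed effects. Dropout of about 15% and the covariance values were assumed. REML and Kenward-Roger were programmed in Python, not SAS.

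| Week 12 quantity | 78 parameters | 79 parameters |
|---|---|---|
| Difference | 0.45337 | 0.45337 |
| Kenward-Roger SE | 0.23064 | 0.23064 |
| Kenward-Roger df | 271.81 | 271.81 |
| Upper 95% bound | 0.90744 | 0.90744 |
| Rank of information matrix | 78 | 78 |

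Two starting values for the 79-parameter fit gave patient variances of 1.41 and 1.81 with the same log-likelihood, estimate, SE and df. The split between R and s is arbitrary, but nothing that is reported depends on it.

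**Other models** (parameters with the random effect / rank).

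- Fallbacks over 12 weeks: TOEPH 24/24, ARH(1) 14/14, CSH 14/14, TOEP 13/12, AR(1) 3/3, CS 3/2. The TOEPH and CSH ranks assume weekly variances that differ.
- Secondary unstructured models: night pain and worst pain over 12 weeks 79/78; measures at four visits 4 × 5 / 2 + 1 = 11, rank 10; BDI-II at three visits 3 × 4 / 2 + 1 = 7, rank 6.

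**The case for a change.** The best case for a change is this. The text names both terms in three places, and nothing corrects it. The plan does not define non-convergence, so a singular-matrix warning after database lock could leave a judgement to be made on the primary analysis. In four of the six fallbacks (TOEPH, ARH(1), CSH, AR(1)) the random effect is not redundant, so keeping or dropping it there gives different models and the SAP does not say which is meant. Deleting one phrase would cost almost nothing.

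The literal reading and the rank count stand. The rest carries less weight.

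- SAP 6.10 identifies its model by the unstructured covariance alone. In the fallback it varies only the within-patient structure, and it gives no structure or fallback for a random effect. SAP 6.14 calls the method a repeated measures approach. Together these point to a model in which patient is the repeated-measures subject. On that reading the fallbacks are unambiguous.
- The trigger in the plan is failure to converge. A warning on a converged fit is not that trigger.
- How SAS 9.2 or later would handle the redundant term is unknown. In the Python routine the 79-parameter fits converged, but that says nothing about SAS.
- An analyst who leaves the term out stays within the plan's rules. Under Protocol 12.2.1 a change to the analysis methods "will require an amendment ONLY if it changes a principal feature of the protocol". Under SAP 6.2 any other change, with its justification, "will be described in the SAP and clinical study report". For the unstructured model, leaving out the term alters nothing that is estimated.

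The fallback ambiguity is real on the literal reading, but it matters only if the unstructured fit truly fails.

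**Conclusion.** The wording is imprecise, but the planned result is unaffected. Read literally, the primary model has 79 covariance parameters of rank 78. The Week 12 difference, Kenward-Roger SE, df and the comparison with 0.51 equal those of the plain unstructured model. The equality of likelihood and estimate is exact algebra and needs no assumption about dropout or variances. The equality of SE and df assumes that the unstructured fit converges and that the software either uses a generalized inverse or sets the patient variance to zero.

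The one route to harm, a needless move to the fallback, has not been shown to occur. No size is given for it here: it would depend on an untested probability in SAS, on whether the random effect is kept in the fallback, and on dropout and covariances that the documents do not state. This is a clerical slip that an experienced programmer resolves by treating patient as the repeated-measures subject. Correcting it would not change the primary conclusion, so no change to the plan is called for.

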6.1. Determination of Sample Size

Approximately 286 patients will be randomized in a 1:1 ratio to duloxetine or pregabalin respectively.

Sample size was calculated in order to have enough statistical power to confirm the non-inferiority of duloxetine to pregabalin based on the primary endpoint, the change from baseline to Week 12 in the weekly mean of the 24-hour average pain score, which will be evaluated using an 11-point NRS in the daily patient diary. Assuming that the treatment difference of the primary endpoint is 0.1 (i.e. duloxetine is superior to pregabalin by 0.1) and that the common standard deviation (SD) of the primary endpoint is 1.82 with a non-inferiority margin of 0.51, 141 patients per group (282, in total) would have a statistical power of 80% to confirm the noninferiority with a 1-sided significance level of 0.025.

The treatment difference could be assumed to be at least 0.1 in this study based on the results such as the double-blind randomized study to comparing duloxetine and pregabalin (the treatment difference [95% confidence interval (CI)]: 0.61 [0.33, 0.90]) (Bouhassira et al. 2014, Marchettini et al. 2016, Tesfaye et al. 2013) and the results of the meta-analysis comparing them indirectly (the treatment difference [95% credible interval]: 0.25 [-0.16, 0.67]) (Quilici et al. 2009) even though there are differences such as treatment periods among the studies.

The noninferiority margin was estimated based on a meta-analysis that applied the DerSimonian-Laird method. Utilizing a phase 3 trial of pregabalin in Japan, which was treated as an evaluation-test in either Japan or the US, this meta-analysis looked at the difference of variation in the average pain score between placebo and pregabalin after 12 weeks of treatment. It was estimated that the difference of the mean value and its 95% CI was 1.03 (0.69, 1.37). The non-inferiority margin for the current study was set using half of the difference of the mean value, 0.51 (that is, 1.03/2). The SD was assumed to be 1.82, based on the pooled analysis results of 1 pregabalin trial and 2 duloxetine trials conducted in Japan.

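### The primary MMRM fits one baseline slope to all 12 weeks; if the true slope changes over time, the Week 12 interval that decides non-inferiority is wider than it need be

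*SAP*

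**What the plan says.** SAP 6.10 gives the primary MMRM fixed effects for treatment, DPNP duration and "week, and treatment-by-week interaction, as well as the continuous fixed covariates of baseline value", with an unstructured within-patient covariance over 12 weekly means. The protocol repeats this model in the Synopsis (Statistical Methods) and in 12.2.6. Neither document has a baseline-by-week term.

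The decision uses one week. The Week 12 difference in LS means (duloxetine minus pregabalin) is estimated with its two-sided 95% interval, and non-inferiority is concluded under this condition: "If the upper bound of the 95% CI does not exceed 0.51".

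SAP 6.11 carries the model over: "The secondary efficacy objectives will be addressed by conducting MMRM analyses". Visit replaces week except for diary items, and the baseline score is left out for CGI-I and PGI-I.

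Two other analyses let the baseline effect be specific to a week. The secondary ANCOVA of change to Week 12 (SAP 6.10, protocol 12.2.6) fits its own slope, but on LOCF or BOCF data. The optional subgroup model in SAP 6.14 adds strata-by-week terms, and baseline pain (<6, ≥6) is one of its strata. Randomisation is stratified by that same split (protocol 9.3).

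**The concern.** The model lets the treatment effect change from week to week but holds the baseline effect fixed. In this design a changing baseline effect is plausible, though not documented. Week 1 is spent on the starting dose, and doses may rise at Weeks 4 and 8 in patients short of 30% improvement. If improvement is roughly proportional to baseline pain, the slope of change on baseline steepens as mean improvement grows.

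If so, the common slope is wrong for Week 12, and the misfit goes into the Week 12 residual variance. Part of the precision that baseline adjustment could give is then lost in the only comparison that decides the trial. The sample size leaves little slack: 282 patients are required, about 286 are planned, and no dropout rate is stated. An interval 0.7% wider uses up information equal to that whole allowance (1.007² = 1.014; 286/282 = 1.014).

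**Working it through.** **Inputs from the documents.** Margin 0.51; assumed true difference 0.1 in favour of duloxetine; SD 1.82 (not stated whether raw or baseline-adjusted); "statistical power of 80% to confirm the noninferiority with a 1-sided significance level of 0.025"; 141 per group required, 143 per arm planned.

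**The plan's own figure.** The distance from the assumed truth to the margin is 0.51 + 0.1 = 0.61. The normal formula gives n = 2 × 1.82² × (1.960 + 0.842)² / 0.61² = 139.7, so 140 per arm. The noncentral t gives 141 (power 80.1%; 80.6% at 143). The stated size is reproduced. At SD 1.82 and 143 per arm the half-width is 1.96 × 1.82 × √(2/143) = 0.422.

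**Formula for the loss.** Let b_t be the true slope of change on baseline in week t and Σ the residual covariance. A single fitted slope converges to

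b* = Σ_t w_t b_t, with w = Σ⁻¹1 / (1′Σ⁻¹1).

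The Week 12 residual variance becomes σ₁₂² + (b₁₂ − b*)² × Var(baseline). With baseline-by-week in the model it is σ₁₂².

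**Assumptions (none is in the documents).** Raw Week 12 SD 1.82, so σ₁₂² = 1.82² − b₁₂² × Var(baseline). Baseline SD 1.3. Slopes drift linearly over 12 weeks. Covariance shapes: exchangeable 0.7 or AR(1) 0.9, each with constant SD or with SD rising linearly from about 55% of its Week 12 value; and a random walk.

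**Worked line.** Drift −0.1 to −0.4, constant SD: σ₁₂² = 3.3124 − 0.16 × 1.69 = 3.042 (SD 1.744). Early and late weeks weigh equally, so b* = −0.25. The variance becomes 3.042 + 0.15² × 1.69 = 3.080 (SD 1.755). The half-width is 0.407 against 0.404.

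Power below is Φ(0.61/(SD × √(2/143)) − 1.96). Each pair shows the common slope first, then baseline-by-week.

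| Drift, Week 1 to 12 | Covariance | b* | SD | Half-width | Wider by | Power % |
|---|---|---|---|---|---|---|
| −0.3, constant | any of the five | −0.30 | 1.778 / 1.778 | 0.412 / 0.412 | 0% | 82.7 / 82.7 |
| −0.1 to −0.4 | constant SD | −0.25 | 1.755 / 1.744 | 0.407 / 0.404 | 0.6% | 83.6 / 84.1 |
| −0.1 to −0.4 | AR(1), growing SD | −0.145 | 1.775 / 1.744 | 0.412 / 0.404 | 1.8% | 82.8 / 84.1 |
| −0.1 to −0.4 | random walk | −0.10 | 1.787 / 1.744 | 0.414 / 0.404 | 2.5% | 82.3 / 84.1 |
| −0.1 to −0.4 | exchangeable, growing SD | 0.02 | 1.829 / 1.744 | 0.424 / 0.404 | 4.8% | 80.5 / 84.1 |
| 0 to −0.5 | constant SD | −0.25 | 1.731 / 1.700 | 0.401 / 0.394 | 1.8% | 84.6 / 85.9 |
| 0 to −0.5 | AR(1), growing SD | −0.075 | 1.788 / 1.700 | 0.414 / 0.394 | 5.2% | 82.3 / 85.9 |
| 0 to −0.5 | random walk | 0.00 | 1.820 / 1.700 | 0.422 / 0.394 | 7.1% | 80.9 / 85.9 |
| 0 to −0.5 | exchangeable, growing SD | 0.20 | 1.931 / 1.700 | 0.448 / 0.394 | 13.6% | 76.2 / 85.9 |

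In the growing-variance rows Week 1 takes 64 to 100% of the slope weight and Week 12 between −19% and 9%. In the constant-SD rows Weeks 1 and 12 weigh the same.

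**Sensitivity to baseline SD.** At 1.6 the worst moderate case is 7.6% wider and the worst strong case 21% wider. Over baseline SDs of 1.0 to 1.6, every case above 10% combines the 0 to −0.5 drift with growing variance. Power falls below 80% (to 74 to 78%) only with that drift, exchangeable correlation and growing SD.

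**Simulation.** Both models were fitted by maximum likelihood with 143 per arm, stratified assignment, baseline SD 1.3, growing SD and 200 trials per setting. The model SE ratio (common slope over baseline-by-week) was 1.01 to 1.04 under moderate drift and 1.04 to 1.11 under strong drift, and similar with about 13% dropout. Mean estimates from the two models differed by 0.01 at most. A separate simulation (1,000 trials per setting, about 13% dropout) gave SE ratios of 1.007, 1.023, 1.049 and 1.090 for assumed baseline-to-Week-12 correlations of 0.50, 0.45, 0.35 and 0.30.

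**The case against.** The planned model is prespecified and valid, and randomisation is stratified on baseline pain. The estimate is essentially unchanged by the extra term, and a wider interval works against declaring non-inferiority. All of that stands.

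The sample size rests on an SD of 1.82 in a two-sample calculation, with no stated credit for baseline adjustment. What is lost is therefore mainly a gain the plan never counted on. That stands too.

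The ANCOVA already fits a Week 12 slope. This helps only in part: because it also changes the handling of missing data, a gap between it and the MMRM would mix the two causes.

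Three stronger readings are tempting, and the documents support none of them:

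- *Week 12 is necessarily adjusted with an early-week slope.* This needs residual variance that grows over the weeks. Under constant variance the slope is an average of early and late weeks. The documents do not say which applies.
- *The reported SE overstates the true sampling error.* The 1,000-trial simulation showed 0.225 reported against 0.216 observed in its most extreme setting. The Monte Carlo error of that SD is about 0.216/√2000 = 0.005, so the gap is under two standard errors. In the 200-trial runs the planned model's SE was above the observed SD in four of eight settings and below it in four.
- *The trial is underpowered because of the model.* The 1,000-trial runs gave 76.1 to 78.4% success under the planned model, but they assume about 13% dropout. Completers alone (143 × 0.87 ≈ 124 per arm) would give Φ(0.61/(1.82 × √(2/124)) − 1.96) ≈ 75% at SD 1.82, whatever the slope. Adding the term raised success by 0.4 to 5.6 points, with the largest gain at the most extreme correlation.

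**Conclusion.** The point holds as a conditional loss of precision. The omission is certain and appears in both documents; its effect in this trial is not known. The Week 12 interval is no wider if the slope is constant, about 0.5 to 5% wider under moderate drift at a baseline SD of 1.3 (0.4 to 7.6% over baseline SDs of 1.0 to 1.6), and more than 10% wider only with strong drift and growing variance. There is no bias and no added risk of a false claim of non-inferiority. Power stays at or above 80% in most full-data scenarios. These sizes rest on the assumed baseline SD, linear drift, covariance shapes and a raw Week 12 SD of 1.82. The change is worth making because it costs almost nothing and any gain falls on the deciding interval.

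**What to change.** Before unblinding:

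- **SAP 6.10:** add the baseline-by-week interaction to the primary MMRM, and keep it in the fallback covariance fits.
- **SAP 6.11:** add baseline-by-visit (baseline-by-week for diary items) to the MMRMs that include a baseline score. CGI-I and PGI-I have none and stay as they are.
- **Protocol Synopsis and 12.2.6:** align the model. Otherwise, record the change and its justification as protocol 12.2.1 and SAP 6.2 require, after deciding whether it alters a principal feature and so needs an amendment. Editing the SAP alone would leave the two documents with different primary models.

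Leave the margin, the Week 12 contrast and the decision rule unchanged.

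The cost is 11 more fixed-effect parameters in the primary model, from 26 (intercept 1, treatment 1, duration 1, week 11, treatment-by-week 11, baseline 1) to 37, with about 286 patients, plus the document revisions. No new data are needed.

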## 12.2.6. Primary Outcome and Methodology

The primary efficacy variable is the change from baseline in the weekly mean of the 24-hour average pain score measured using an 11-point NRS in the daily patient diary.

A mixed-model repeated measures (MMRM) analysis will be the primary analytical technique to assess mean change in efficacy measures. The MMRM model will include the random effect of patient and fixed categorical effects of treatment, duration of DPNP (<2 years, ≥2years), week, and treatment-by-week interaction, as well as the continuous fixed covariates of baseline value. An unstructured covariance structure will be used to model the within-patient errors. A Kenward-Rogers correction (Kenward and Roger 1997) will be used to estimate denominator degrees of freedom.

The difference in LS mean between treatments (duloxetine minus pregabalin) at Week 12, along with its 2-sided 95% CI, will be calculated, based on the model. If the upper bound of the 95% CI does not exceed 0.51, it will be concluded that duloxetine is not inferior to pregabalin.

If the model with unstructured covariance structure fails to converge, the sandwich estimator (Lu and Mehrotra 2010) will be used to estimate the standard errors of the fixed effects parameters and the model will be fit using covariance structures of the following order until convergence is met:

- heterogeneous toeplitz type = toeph
- heterogeneous autoregressive (1st order) type = arh(1)
- heterogeneous compound symmetric type = cs(h)
- toeplitz type = toep
- autoregressive (1st order) type = ar(1)
- compound symmetric type = cs

If the sandwich estimator is used, the Kenward-Roger approximation for denominator degrees of freedom cannot be used; instead, the denominator degrees of freedom will be partitioned into between-subject and within-subject portions (denoted by DDFM= BETWITHIN in the MODEL statement).

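### If the unstructured fit fails, the plan goes straight to structured covariances and repairs only the standard errors; the full 12-week unstructured fit should be retried first, without the redundant patient random effect

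*SAP*

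**What the plan says.** The primary analysis is a mixed model for repeated measures on the weekly mean pain score at Weeks 1 to 12. It has an unstructured within-patient covariance and Kenward-Roger degrees of freedom, and it also lists a random effect for patient. The decision rests on one contrast, duloxetine minus pregabalin at Week 12: "If the upper bound of the 95% CI does not exceed 0.51, it will be concluded that duloxetine is not inferior to pregabalin".

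The fallback is the same in both documents. Protocol 12.2.6 opens it with "If the model with unstructured covariance structure fails to converge". SAP 6.10 then asks that "the sandwich estimator be used to estimate the standard errors of the fixed effects parameters", and both refit with TOEPH, ARH(1), CSH, TOEP, AR(1) and CS in that order, stopping at the first that converges. Kenward-Roger is replaced by between-within degrees of freedom. Neither document tries to rescue the unstructured fit before leaving it.

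The prespecified robustness analyses are ANCOVA with LOCF, ANCOVA with BOCF (and LOCF for the other missing cases), and the per-protocol set.

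**The concern.** With complete data, a wrong working covariance costs little beyond precision, and sandwich standard errors deal with the variance. With dropout, the model fills in Week 12 for patients who left by regressing on their earlier weeks, and the regression coefficients come from the fitted covariance. If the imposed structure is wrong, those coefficients are wrong and the Week 12 mean moves. A sandwich estimator changes the standard error and leaves the estimate where it is. A correctly fitted unstructured matrix avoids this under missing-at-random dropout.

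The protocol creates exits of both relevant kinds. Section 7.1 has non-responders who are not escalated considered for discontinuation, and patients who cannot tolerate an increase discontinued. The first exit is tied to pain and the second to tolerability. Nothing ensures the same mix in the two arms.

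At stake is the single non-inferiority decision. None of the robustness analyses examines the covariance choice.

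**Working it through.** **1. Reproduce the plan's sample size.** Inputs from SAP 6.1: "common standard deviation (SD) of the primary endpoint is 1.82"; margin 0.51; "duloxetine is superior to pregabalin by 0.1"; test "with a 1-sided significance level of 0.025"; result "141 patients per group (282, in total) would have a statistical power of 80" per cent.

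n per group = 2 × SD² × (1.960 + 0.842)² / (0.51 + 0.10)² = 2 × 3.3124 × 7.849 / 0.3721 = 139.7, so 140. The plan's 141 is reproduced to within one patient. With 143 per arm ("Approximately 286 patients will be randomized in a 1:1 ratio to duloxetine or pregabalin respectively"), SE = 1.82 × √(2/143) = 0.215 before any dropout, and power = Φ(0.61/0.215 − 1.96), about 81%.

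**2. Identifiability.** Twelve weeks give 12 × 13 / 2 = 78 distinct covariance elements. Write the total covariance as V = σ²·11ᵀ + R, with R unstructured. Replacing σ² by σ² + c and R by R − c·11ᵀ leaves V unchanged. Coded literally, the model has 79 parameters for 78 quantities, and the likelihood cannot separate the patient variance from R.

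**3. Mechanism.** To first order, the Week 12 bias in one arm is π × (b_fitted − b_true) × d. Here π is the fraction who drop out, b the regression of Week 12 on the earlier weeks, and d the leavers' average departure from the arm mean. If leaving is unrelated to pain, d is 0. If both arms share π, b and d, the terms cancel in the contrast. Otherwise the sign depends on which arm loses its worse patients and on whether the structure over- or under-states the regression.

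**4. Size.** The documents give neither a dropout rate nor within-patient correlations, so both are assumptions. The check was by large-sample simulation (60,000 per arm, Week 12 SD 1.82) under several assumed true covariances: random intercept and slope, random-walk type, stationary, and a break at Weeks 4 and 8. Dropout was monotone and depended on the last observed pain change. Covariates were omitted. Each structure was fitted without a separate patient effect.

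Absolute bias at 20% dropout per arm, pain-related in one arm and random in the other:

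| Structure, in the plan's order | Bias | Share of 0.51 |
|---|---|---|
| Unstructured retained | at most 0.01 | 2% |
| TOEPH | 0 to 0.07 | 0 to 14% |
| ARH(1) | 0.06 to 0.17 | 12 to 33% |
| CSH | 0 to 0.05 | 0 to 10% |
| TOEP | 0 to 0.09 | 0 to 18% |
| AR(1) | 0.08 to 0.17 | 16 to 33% |
| CS | 0.03 to 0.11 | 6 to 22% |

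Other assumptions:
- Same pattern at 10% dropout: TOEPH up to 0.03, largest for any structure 0.08.
- Same pattern at 30%: TOEPH up to 0.075, AR(1) up to 0.23.
- 20% dropout acting in opposite directions by arm: TOEPH up to 0.09, AR(1) up to 0.26.
- Same pain-related rule in both arms with the true difference at the margin: TOEPH up to 0.02, others up to 0.05.
- Same rule with equal means, or dropout unrelated to pain (10% against 30%): about 0.

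**5. Consequence.** One-sided error at a true difference of 0.51 = Φ(−1.96 + bias/SE), for a bias towards duloxetine with SE 0.215:
- bias 0.05: Φ(−1.727) = 4.2%
- bias 0.07: Φ(−1.634) = 5.1%
- bias 0.17: Φ(−1.169) = 12.1%

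Dropout would widen the SE somewhat; at an assumed SE of 0.23, a bias of 0.05 gives 4.1%. A bias of 0.05 against duloxetine would instead cut power to Φ((0.61 − 0.05)/0.215 − 1.96) = 74%.

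**The case against.** The fallback is prespecified, ordered and fixed before database lock. It starts with a flexible structure and stops at the first that converges, and the protocol cites a methods paper for the sandwich step. All of that stands. So ARH(1) is reached only if the unstructured and TOEPH fits both fail, and AR(1) only after five failures. The realistic figure is the TOEPH one.

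Non-convergence is not shown to be likely from the parameter count. In 100 simulated trials of 143 per arm (20% dropout, 3% intermittent missingness, no patient effect, EM algorithm), the 12 × 12 unstructured fit converged every time. That is not the sponsor's REML software, but it means that 78 parameters alone do not make the case. The patient effect is the clearer hazard, and even there the wording may only be a loose description of repeated measures within patient.

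Keeping a patient effect in the fallback fits also changes the figures. In one check at 20% dropout it cut the bias from 0.114 to 0.054 for ARH(1) and from 0.124 to 0.058 for AR(1).

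What the objection does not remove is the gap itself. The plan leaves the unstructured model at the first failure, and no other planned analysis would show the effect on the estimate.

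**Conclusion.** The point holds as a conditional weakness with an almost free remedy. It needs three things together: a failed unstructured fit, a structure that misrepresents the true covariance, and dropout that depends on pain and acts differently by arm (or the same rule with clearly different means, where the bias is smaller). Given these, and assuming 20% dropout per arm that is pain-related in one arm only, the Week 12 difference shifts by about 0 to 0.07 under the first fallback and by up to about 0.17 under the autoregressive ones.

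A reader might infer more: that the bias has a known ceiling such as a fifth of the margin (0.102), that it favours non-inferiority, or that any dropout produces it. The documents support none of these. They give no dropout rates or correlations, so no ceiling can be derived, and the assumed scenarios run from 0 to about half the margin. The direction depends on which arm loses patients for pain and on the structure reached. Dropout by the same mechanism with similar means gives almost no bias.

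**What to change.** In SAP 6.10, and in Protocol 12.2.6 if it is amended:

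1. State that no separate patient random effect is fitted when the unstructured matrix is used.
2. Before the existing list, add one step. If the unstructured fit fails, refit the same 12-week unstructured covariance with Fisher scoring, taking starting values from a Cholesky fit (TYPE=FA0(12)) and keeping Kenward-Roger.
3. Use the structured list with sandwich errors only if that step also fails.

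Do not insert an unstructured fit on the even weeks alone, although its 6 × 7 / 2 = 21 parameters look attractive. It discards odd-week scores on which dropout depends. At 20% dropout it gave a bias of 0.05 to 0.07, no better than TOEPH (0.056 against 0.037 in one like-for-like check).

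The cost is a few lines of SAP text and code, settled before unblinding. No patients or extra data are needed.
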